- ³ EQ-5D-3L (Appendix 6) will be assessed at the week 16 visit only, and end-of-study treatment visit. For placebo patients crossing over to open-label darolutamide, EQ-5D-3L will be assessed at the start of open-label treatment instead of end-of-study treatment visit. If the end of the double-blind treatment period occurs less than 16 weeks from the start of study treatment, the EQ-5D-3L assessment is required in the first 16 weeks of open-label darolutamide treatment.
- ⁴ Also height will be recorded at the screening visit.
- ⁵ A triplicate 12-lead ECG including HR in a supine position after at least 10 minutes rest will be performed at screening and on day 1 for all patients. For patients participating to PK sampling, a triplicate 12-lead ECG will be also performed before PK samplings. The 3 consecutive recordings will be performed within approximately 5 minutes. BP and HR (unless recorded by ECG) in a supine position after at least 10 minutes rest. The assessments will be done in the following order: ECGs and vital signs before any type of blood draw. For those patients who do not participate to PK sampling, 12-lead ECG will be obtained once on visits after day 1. See Section 6.6.2.1 for further details.
- ⁶ See Section 6.2 for PK procedures (blood sampling and recording of 12-lead ECG and vital signs) at study centres participating in PK sample collection. If PK sampling is not feasible during these visits, later visits may be used for PK procedures.
- ⁷ Patients will be instructed to complete the diary for 6 days (-6 to -1 day) before day 1 and every 16-week visits until documented pain progression.

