Collection of AEs and SAEs considered to be related to study treatment or procedures	X	X	X ⁵	X ⁵
Collection of concomitant treatments used to treat new related or unresolved related AEs	X	X	X	X
Darolutamide dispensing and accountability			X	X ⁷
First SSE	X	X	X	X
First prostate cancer-related invasive procedure for prostate cancer	X	X	X	X
Survival status ⁸	X	X	X	X
Serum PSA	X		X ⁶	
Chest, abdomen, and pelvic CT/MRI	X		X ⁶	
Bone scan ⁴	X		X ⁶	

Abbreviations: ECOG = Eastern Cooperative Oncology Group; EOS = end-of-study; PSA = prostate-specific antigen; SSE = symptomatic skeletal event

* Note: In case a patient initiates a prohibited treatment during the open-label treatment phase before metastasis confirmed by local reading, the patient must discontinue study treatment and will be followed for survival until the end of the study (see Section 4.7.1 for additional details).

¹ Until metastasis, death, transition to a roll-over study, or the end of the study

² Until death or the end of the study

³ Patients will be instructed to complete the diary for 6 days before each 16-week visit until documented pain progression. Pain medications will be recorded on CRFs at each 16-week visit until documented pain progression.

⁴ New lesion(s) in bone scan must be confirmed by CT/MRI (whichever imaging was conducted at screening for soft tissue) or x-ray. If confirmatory scan is negative (does not confirm progression), the patient will continue to visit study centre as specified in the study event table.

- ⁵ For placebo patients crossing over to open-label darolutamide, all AEs and SAEs irrespective of relatedness will be captured.
- ⁶ Placebo patients crossing over to open-label darolutamide will have central PSA testing and local imaging, radiology .
- ⁷ Only drug accountability performed at the end-of-study treatment visit.
- ⁸ Survival data will also be collected through an additional survival sweep. All patients considered alive shortly after the database cut-off date for the MFS analysis and prior to any subsequent analysis of OS will be contacted for survival status.

Patients initiating a prohibited treatment before confirmed metastasis will be followed only for survival status every 16 weeks until the end of the study.

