6.3.2.4 Time to pain progression

Pain progression is defined as an increase of ≥ 2 points from baseline (day 1 score) in question 3 of BPI-SF (related to the worst pain in the last 24 hours) taken as a 7-day average, or initiation of short or long-acting opioids for pain, whichever comes first.

Pain will be assessed with the BPI-SF questionnaire (Appendix 4) during the visit, pain diary entries from 6 days preceding the visit and opioid use from baseline until documented pain progression. The pain diary consists of 6 copies of BPI-SF questionnaire.

Initiation or change in the use of other non-opioid analgesics is not used in the analysis of pain progression.

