### 6.2.2.2 Time to pain progression

Time to pain progression (PP) is defined as time from randomization to pain progression, where progression is defined as an increase of 2 or more points from baseline in question 3 of the Brief Pain Inventory-Short Form questionnaire (BPI-SF) related to the worst pain in the last 24 hours taken as a 7-day average for post-baseline scores, or initiation of short or long-acting opioids for pain, whichever comes first. Initiation or change in the use of other non-opioid analgesics is not used in the analysis of pain progression.

List of opioids for cancer pain is available in Appendix 9.10.

Questionnaire BPI-SF is detailed in Appendix 9.2.

A minimum number of 4 completed daily reports at each reporting time point out of the 7 days required per protocol are needed to consider valid the assessment.

If the complete date of the assessment is not known, but the year and month are available, day 15 of the month will be used for the calculation.

Table 10 will be used for calculating the time to first pain progression. Time to Pain progression = End Date – Date of Randomization +1.

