In case of missing responses for one or more items, subscale scores can be prorated. This is done by multiplying the sum of the subscale by the number of items in the scale, then dividing the number of items actually answered. Prorating of scores is acceptable as long as more than 50% of the items are answered (assuming that the score of missing items are similar to those of non-missing items). If less than or equal to 50% of the items are answered for any domain, then the score of that specific domain is set to missing. The FACT-P total score is then calculated as the sum of the un-weighted subscale scores. Moreover, the FACT-P total score is set to missing if the related overall item response rate is less than or equal to 80%.

The total score is then calculated as the sum of the un-weighted subscale scores. A total score is calculated if all of the component subscales have a valid score.

Rate of the question GS7 'I am satisfied with my sex life' in the SWB domain will be used independent of the answer documented in the question Q1 "Regardless of your current level of sexual activity, please answer the following question. If you prefer not to answer it, please check this box and go to the next section".

3) The **BPI-SF** questionnaire assesses clinical pain related to cancer, it is a validated tool. Two scores will be derived: the pain severity and the pain interference.

Questionnaire is completed daily over a 7-day period. Averages during the period of reporting are calculated. If fewer than 4 reports out of the 7 days are available at the planned time point for assessment, this would constitute missing data.

The BPI assesses pain at its “worst” “least” “average” and “right now” (current pain). To derive the “pain severity” score a mean score of the 4 questions (questions 3 to 6 from the BPI-SF) related to pain will be created. In case of one or more missing information the “pain severity” score will be assessed to missing.

The BPI measures how much pain has interfered with seven daily activities, including general activity, walking ability, normal work, mood, enjoyment of life, relations with others, and sleep (question 9 from the BPI-SF). BPI “pain interference” is scored as the mean of the seven interference items. This mean can be used if more than 50% or four of seven, of the total items have been completed on a given administration.

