#### Calculation of Time (AUC):

AUC will not be calculated if baseline data is missing.

The trapezoidal rule will be used to derive the AUC for a patient for the FACT-P total and subscale score, EQ-5D-3L index score, VAS score, BPI-SF pain severity and interference scores and EORTC-QLQ-PR25 urinary symptoms score. The time-adjusted AUC will be calculated by dividing the AUC by the duration (in days) over the treatment period. When calculating the AUC, the exact date of completion of the questionnaires should be plotted and the duration will be calculated in days. The time adjusted AUC for the FACT-P subscale scores and total score, EQ-5D-3L index score, VAS score, BPI-SF pain severity and interference scores and EORTC-QLQ-PR25 urinary symptoms score for an individual patient over a period of time [Ta, Tb] will be calculated as follows:

$$AUC_{a-b} = \frac{1}{2(T_b - T_a)} \sum_{i=a}^{b-1} (PRO_i + PRO_{i+1})(T_{i+1} - T_i)$$

Where  $PRO_i$  is the PRO measurement at time  $T_i$  ( $i=a \dots b$ ).

To test the treatment effect, a mixed linear model (random coefficient model) will be used for the EQ-5D-3L index score and VAS score, and for the FACT-P total score, BPI-SF pain severity and interference scores and the subscale scores and the EORTC-QLQ-PR25 urinary symptoms score.

For patients with missing baseline FACT-P, PCS, EORTC-QLQ-PR25 urinary symptoms, EQ-5D-3L scores, time to deterioration will not be calculated.

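### BPI-SF pain scores after pain progression are missing by rule, so the tertiary pain AUC, by-visit means and mixed model describe pain only up to the progression visit

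*SAP*

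**What the plan says.** **Score and missing-data rule.** SAP v4.2, 6.2.3.9, item 3, has the BPI-SF completed daily over seven days. "Averages during the period of reporting are calculated", and then: "If fewer than 4 reports out of the 7 days are available at the planned time point for assessment, this would constitute missing data". SAP 6.2.2.2 sets the same minimum for time to pain progression: "A minimum number of 4 completed daily reports at each reporting time point out of the 7 days required per protocol are needed".

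**Source of the seven reports.** Protocol 6.3.2.4: "The pain diary consists of 6 copies of BPI-SF questionnaire". The seventh report is the questionnaire completed at the visit.

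**When the diary stops.** Protocol Table 3, footnote 7, tells patients to "complete the diary for 6 days (-6 to -1 day) before day 1 and every 16-week visits until documented pain progression". Table 4, footnote 3, says: "Patients will be instructed to complete the diary for 6 days before each 16-week visit until documented pain progression". SAP Appendix 9.1 repeats both. The BPI-SF row for the visit questionnaire has no such limit in either protocol table.

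**Treatment after pain progression.** Protocol 4.7.2 lists metastasis and intolerable adverse events as the required reasons for withdrawal. Pain progression is not among them.

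**Use of the scores.** SAP 6.2.3.9 puts severity and interference into by-visit summaries, an ANCOVA on time-adjusted AUC from all available data, and a random coefficient model. On the divisor: "The time-adjusted AUC will be calculated by dividing the AUC by the duration (in days) over the treatment period". The displayed formula divides by Tb minus Ta and does not define Tb. SAP 6.2.3 gives tertiary p-values an informative role only.

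**The concern.** Each rule is reasonable alone. The diary stop suits a time-to-first-event endpoint, and the 4-of-7 minimum suits an average. Together they remove every severity and interference score after the progression visit, and what triggers the removal is worsening pain or the start of an opioid.

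The by-visit means therefore become means among men who have not yet progressed, and the AUC becomes average pain up to progression. The SAP labels neither in that way. It has no single-report rule, no imputation and no sensitivity analysis for later visits; it only tabulates missing assessments by arm. A reader would take the results as pain over the treatment period. If the arms progress at different rates, the comparison is also distorted.

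**Working it through.** **1. Count of reports.** Before progression: 6 diary copies + 1 visit BPI-SF = 7, which reproduces the SAP's seven. After progression: 0 + at most 1 = 1, and 1 < 4. Every later planned time point is missing. If Protocol 6.3.2.4 is read as also ending the visit questionnaire, the count is 0 and the result is the same. The progression visit itself is kept.

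**2. Share of on-treatment visits lost.** From the documents: median placebo MFS 25 months, MFS hazard ratio 0.65 (implied darolutamide median 25/0.65 = 38.5 months), 40 months' accrual, 16-weekly visits. Assumed, because the documents are silent: placebo median time to pain progression 20 or 40 months, a range of pain hazard ratios, cut-off 48 months after first patient in, exponential times, and pain independent of metastasis. Dropout is not modelled. Per man, visits lost = max(0, last visit number − progression visit number), summed and divided by total visits.

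| Pain HR | Placebo median 20 mo: placebo vs darolutamide | Placebo median 40 mo: placebo vs darolutamide |
|---|---|---|
| 0.5 | 27.7% vs 17.3% | 16.0% vs 9.3% |
| 0.65 | 27.9% vs 21.5% | 16.1% vs 11.9% |
| 0.8 | 27.6% vs 25.3% | 15.8% vs 14.2% |
| 1.0 | 27.7% vs 29.6% | 16.0% vs 17.3% |

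Cut-offs of 44 and 54 months give the same pattern. At HR 1.0 the loss is slightly larger on darolutamide, because those men stay on treatment longer.

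**3. Effect on the AUC, step model.** Assumed: pain HR 0.65, placebo pain median 20 to 45 months, every progressor rises 2 points and then stays flat or gains 0.1 per month. The true difference (darolutamide minus placebo) of −0.06 to −0.12 becomes −0.03 to −0.06. That is a shift of about 0.03 to 0.06 points, or roughly 40 to 55% of the difference. If the truncated area is divided by the whole treatment period, the shrinkage is 73 to 79%.

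**4. Effect on the AUC, slope model.** Assumed: linear pain with man-to-man variation, stop at the first observed rise of 2 or more, on treatment, cut-off 48 months. Differences are placebo minus darolutamide.

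| Slopes per month, placebo / darolutamide | Full data | Truncated, divided by Tb − Ta | Truncated, divided by whole period |
|---|---|---|---|
| 0.08 / 0.05 | 0.206 | 0.140 | 0.071 |
| 0.05 / 0.035 | 0.057 | 0.045 | 0.039 |
| 0.05 / 0.05 | −0.077 | −0.033 | 0.016 |

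Row 1 loses 0.206 − 0.140 = 0.066 (32%), or 0.206 − 0.071 = 0.135 (66%) with the whole-period divisor. Row 2 loses 0.057 − 0.045 = 0.012 (21%). In row 3, with equal slopes, truncation moves the contrast in darolutamide's favour by 0.077 − 0.033 = 0.044. The direction therefore depends on the true pain effect.

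**The case against.** - **The mixed model copes.** A reader might infer that it is as biased as the AUC. The documents do not support that. The progression visit stays in, so when a recorded rise triggers the stop the model has seen that rise. In a simulation with assumed linear random slopes, the slope difference was −0.0208 with full data and −0.0214 truncated, with about 14% and 12% of visits lost. This stands for score-triggered stops. It does not cover opioid starts, which need no score rise.
- **Placebo need not lose more.** A reader might take a heavier placebo loss as given. No pain-progression rates are stated, and 0.65 is the planned hazard ratio for MFS, not for pain. The heavier loss holds only if darolutamide delays pain progression. That is the trial's objective, not a stated fact.
- **The size is overstated by the inputs.** Pain may not be high after an opioid start; if half of progressors have no rise, the bias roughly halves. The protocol links bone pain to metastasis, which ends treatment. If half of pain progression follows metastasis, lost on-treatment time falls to about 6 to 11% on placebo and 5 to 9% on darolutamide. Both points stand.
- **The stop was intended, and the schedule is not uniform.** The Amendment 1 history records a deliberate change to end pain data at progression. Protocol 6.1.2.4 and 6.1.3 list diary handling without repeating the stop, and one Table 4 cell lacks the footnote. Sites might therefore collect more than the footnotes require, but that does not remove the stop rule, and the SAP does not rely on it.
- **The stakes are low.** These analyses are tertiary, outside the testing hierarchy, and not among the quality-of-life endpoints in Protocol 7.7.3. This stands and limits the weight of the point.

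**Conclusion.** The conflict holds on the text and needs no assumption: after documented pain progression no BPI-SF severity or interference score can be valid under the 4-of-7 rule, although treatment continues and a visit questionnaire is scheduled. This is an outcome-dependent deletion that follows from carrying out the plan as written.

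The effect on the arm comparison is conditional. If darolutamide delays pain progression, placebo loses the larger share of visits and the AUC difference is probably understated, by about 0.03 to 0.06 points in the step model and 0.01 to 0.07 in the slope model. Both are small beside the 2-point progression threshold. With no pain benefit the direction can reverse. The 40 to 55% shrinkage should not be quoted alone: it is a ratio of small numbers and assumes a lasting 2-point rise in every progressor and independence from metastasis.

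MFS and time to pain progression are unaffected; the latter needs only data up to the first progression. The change is worth making because it is cheap, but no confirmatory conclusion depends on it.

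**What to change.** 1. In SAP 6.2.3.9, add a BPI-SF severity and interference AUC and mixed-model analysis that uses the visit-day BPI-SF at every scheduled visit, before and after progression alike. Report it beside the 7-day-average analysis rather than in its place, so that valid diary data are not discarded.
2. Label the 7-day-average AUC, by-visit means and mixed model as pain up to progression.
3. Define Tb as the date of the last valid assessment, so that a truncated area is not divided by the whole treatment period.
4. Keep the 4-of-7 rule for time to pain progression in SAP 6.2.2.2.
5. Reconcile Protocol 6.3.2.4 with Tables 3 and 4 so that the visit BPI-SF clearly continues after pain progression.

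Cost: SAP and protocol wording and one more tertiary analysis to program. Tables 3 and 4 already schedule the questionnaire. A single-day score is noisier than a 7-day mean, which is a further reason to show both.

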#### **PRO analyses:**

PRO data as measured by the FACT-P, the EQ-5D-3L, the EORTC-QLQ-PR25 and the BPI-SF will be analyzed to assess differences in HRQoL and health utility values between treatment arms based on time-adjusted area under the curve (AUC) using all available data.

The PRO analyses will be performed for the patients in the FAS. Statistical tests will be performed with a 2 sided type I error of 5%.

Descriptive statistics on observed data will be presented for the FACT-P questionnaire (each domain score including the PCS and the FACT-P total score), for the EQ-5D-3L index score

(utility value) and visual analog scale score (VAS), for the EORTC-QLQ-PR25 questionnaire (each subscale score) and for BPI-SF questionnaire (pain severity and pain interference scores) at each assessment time and for change from baseline by treatment group. Questionnaires under unscheduled visits and not planned visits per protocol will not be displayed in the descriptive tables. Analyses will be done for patients with baseline assessments.

The frequency for missing health related quality of life (HRQoL) assessment by treatment group will be summarized.

An analysis of covariance (ANCOVA) model will be used to estimate the mean difference in the time-adjusted Area under Curve (AUC) between the two treatment groups, with covariates for baseline PRO scores and stratification factors as recorded in the IVRS data.

Least-square mean estimates, standard errors and 95% CIs will be estimated for each treatment group and for the treatment group difference.

#### Calculation of Time (AUC):

AUC will not be calculated if baseline data is missing.

The trapezoidal rule will be used to derive the AUC for a patient for the FACT-P total and subscale score, EQ-5D-3L index score, VAS score, BPI-SF pain severity and interference scores and EORTC-QLQ-PR25 urinary symptoms score. The time-adjusted AUC will be calculated by dividing the AUC by the duration (in days) over the treatment period. When calculating the AUC, the exact date of completion of the questionnaires should be plotted and the duration will be calculated in days. The time adjusted AUC for the FACT-P subscale scores and total score, EQ-5D-3L index score, VAS score, BPI-SF pain severity and interference scores and EORTC-QLQ-PR25 urinary symptoms score for an individual patient over a period of time [Ta, Tb] will be calculated as follows:

$$AUC_{a-b} = \frac{1}{2(T_b - T_a)} \sum_{i=a}^{b-1} (PRO_i + PRO_{i+1})(T_{i+1} - T_i)$$

Where  $PRO_i$  is the PRO measurement at time  $T_i$  ( $i=a \dots b$ ).

To test the treatment effect, a mixed linear model (random coefficient model) will be used for the EQ-5D-3L index score and VAS score, and for the FACT-P total score, BPI-SF pain severity and interference scores and the subscale scores and the EORTC-QLQ-PR25 urinary symptoms score.

For patients with missing baseline FACT-P, PCS, EORTC-QLQ-PR25 urinary symptoms, EQ-5D-3L scores, time to deterioration will not be calculated.

### 6.2.3.9.1 Percent of patients with deterioration of FACT-P total score at 16 weeks

Patients will be defined as having total QoL deterioration, if they experience a decrease of  $\geq 10$  points in FACT-P total score at 16 weeks compared with baseline.

Deterioration from baseline in FACT-P total score will be compared between treatment arms using a Cochran-Mantel-Haenszel test stratified by stratification factor of PSADT ( $\leq 6$  vs.  $>6$  months) and use of osteoclast-targeted therapy (yes vs. no) at randomization.

Analysis will be created on both sub-sets of patients:

- FAS,
- FAS excluding patients with no visit at week16.

### 6.2.3.9.2 Time to deterioration in PCS subscale score

Time to deterioration for the FACT-P PCS score: a deterioration being defined as a 3 point or more decline in the PCS score.

A patient’s time to deterioration will be defined as the time from randomization to the deterioration date. For patients with no symptomatic deterioration at the time of the analysis, the time to deterioration will be censored at the date of the last FACT-P PCS valid assessment.

Table 20 will be used for calculating the time to deterioration in PCS. Time to Deterioration in PCS = End Date - Date of randomization + 1

**Table 20: Censoring Rules for time to deterioration in PCS**

Situation	End Date on or prior to cut-off date	Censored
No baseline or post-baseline PCS assessment	Date of randomization	Yes
No deterioration in PCS	Last PCS assessment date	Yes
Patient had a deterioration in PCS	The date of first observation of deterioration in PCS	No

This endpoint is selected from the ADTTE dataset using variable PARAMCD equal to ‘FACTDETP’.

Times to deterioration will be displayed by the product-limit estimates of the survival distribution functions (Kaplan-Meier) for each treatment group: N, total censored, total failed, survival time (median and its 95% CI, range), deterioration-free rate at 12, 24, 36 etc.,

months, KM curves. The hazard ratio darolutamide over placebo, its 95% CI will be generated from the Cox model.

